## APPENDIX F: Pharmacokinetic Study Sample Handling and Shipment

### 1.1 Venetoclax and OATP1B1 Biomarker Plasma Pharmacokinetic Samples

- The plasma pharmacokinetic profile of venetoclax and OATP1B1 biomarker will be characterized by collecting blood samples (as outlined in the Study Calendar and in the separate PK study worksheet uploaded at the Cancer Trials Support Unit website [www.ctsu.org](http://www.ctsu.org)).
- Collection of Specimen(s): patients will have 4 mL samples of blood collected in tubes containing K2 EDTA as an anticoagulant (purple top) at the time points specified below:
  - **Baseline**
  - **Cycle 1 Day 14**
    - **Pre-venetoclax**
    - **1 h post venetoclax**
    - **2 h post venetoclax**
    - **4 h post venetoclax**
    - **7 h post venetoclax**
    - **24h post venetoclax**

- Obtain venous blood by standard phlebotomy technique from a peripheral access point. **NOTE:** Suggest using a minimum 18G needle to avoid sample hemolysis.
  - Obtain venous blood by standard phlebotomy technique from a peripheral access point.
- Fill-up the tubes as much as possible until blood flow stops.
- GENTLY invert each tube several times (8-10 times) immediately after collection to avoid sample hemolysis.
- Place samples immediately **on ice** after collection; samples must be processed **within 30 minutes**.

#### 1.1.1 Handling of Specimens(s)

### Processing instructions

1. Invert sample 8-10 times immediately before processing.
2. Centrifuge at ~1000-1300 x g (i.e., RCF, **not RPM**) for 10 minutes in swinging bucket (SW) or 15 minutes in a fixed angle (FA) rotor at 4°C in a refrigerated centrifuge. Make sure that the centrifuge reaches speed and is maintained throughout the entire spin.
3. Carefully remove tube from centrifuge.
4. Using a pipette, transfer equal aliquots of plasma into 2-3 labeled 1.2 mL cryovials (e.g., preferred are external thread, conical self-standing vials like Corning™ 430658 or ), not exceeding ~1 mL per cryovial.
5. Label samples as (drug) (matrix) (purpose), including protocol number (#10417), unique patient ID assigned at registration, date of collection, draw time, time point, protocol time point, and initials.
6. Store plasma samples at -70°C or below until shipment.

### 1.2 Nivolumab Serum Pharmacokinetic Samples

- The plasma pharmacokinetic profile of nivolumab will be characterized by collecting blood samples (as outlined in the Study Calendar and in the separate PK study worksheet uploaded at the Cancer Trials Support Unit website [www.ctsu.org](http://www.ctsu.org)).

- Collection of Specimen(s): patients will have 3 mL samples of blood collected in tubes containing heparin as an anticoagulant (red top) at the time points specified below:

- **Cycle 1 Day 14**
  - **Pre-nivolumab infusion**
    - 4h after end of nivolumab infusion
- **Induction Cycle 2 Day 1**
  - **Pre-nivolumab infusion**
    - 4h after end of nivolumab infusion
- **Maintenance Cycle 1 (Day 1)**
  - **Pre-nivolumab infusion**
    - 4h after end of nivolumab infusion
- **Maintenance Cycle 3 (Day 14)**
  - **Pre-nivolumab infusion**
    - 4h after end of nivolumab infusion
- **End of Treatment/Relapse**
  - ~ 2 weeks after last nivolumab infusion
  - Obtain venous blood by standard phlebotomy technique from a peripheral access point. NOTE: Suggest using a minimum 18G needle to avoid sample hemolysis.
    - Obtain venous blood by standard phlebotomy technique from a peripheral access point.
  - Fill-up the tubes as much as possible until blood flow stops.
  - GENTLY invert each tube several times (8-10 times) immediately after collection and then allow blood to clot for 30-60 minutes at room temperature before centrifugation.

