## 5. BIOMARKER, CORRELATIVE, AND SPECIAL STUDIES

### 5.1 Summary Table for Specimen Collection

Time Point	Specimen	Send Specimens To:
Baseline		
Pre-venetoclax/azole	
 
4 mL Peripheral Blood (EDTA-containing vacutainer) – OATP1B1 plasma biomarker
 
	OSU PharmacoAnalytical Shared Resource for ChOP-KC
	
 
10 mL of bone marrow aspirate in sodium heparin tubes (mandatory)
 
15 mL blood in ACD tubes (mandatory)
 
	Ohio State Leukemia Tissue Bank
	
 
Correlatives: Flow cytometry, Cytogenetics, Next-generation sequencing, Tetramer Analysis, and DNA methylation
 
	
Cycle 1 Day 14 (C1D14)		
Pre-venetoclax, 1h, 2, 4, 7h, 24h	
 
4 mL Peripheral Blood (EDTA-containing vacutainer) – Venetoclax plasma levels, OATP1B1 plasma biomarker assay
 
	OSU PharmacoAnalytical Shared Resource for ChOP-KC
Pre-nivolumab, 4h after end of infusion	
 
3 mL Peripheral Blood (red top vacutainer) – Nivolumab serum levels
 
	
Day 28 +/- 1 day of cycles 1, 2, and 3		
	
 
10 mL of bone marrow aspirate in sodium heparin tubes (mandatory)
 
15 mL blood in ACD tubes (mandatory)
 
	Ohio State Leukemia Tissue Bank
	
 
Correlatives: Flow cytometry, Cytogenetics, Next-generation sequencing, Tetramer Analysis, and DNA methylation
 
	
Day 28 +/- 1 day every 3 cycles starting with cycle 6 (ex. Cycles 6, 9, 12...)		
	
 
10 mL of bone marrow aspirate in sodium heparin tubes (mandatory)
 
15 mL blood in ACD tubes (mandatory)
 
	Ohio State Leukemia Tissue Bank
	
 
Correlatives: Flow cytometry, Cytogenetics, Next-generation sequencing, Tetramer Analysis, and DNA methylation
 
	
Day 28 +/- 1 day of end of every cycle starting with cycle 4 (excluding cycles 6, 9, 12... as above)		
	
 
10 mL blood in ACD tubes (mandatory)
 
	Ohio State Leukemia Tissue Bank
	
 
Correlatives: DNA methylation
 
	
Induction Cycle 2 Day 1		

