## 5.4 Specimen Collection

### 5.4.1.1 Collection of Bone Marrow Aspirate in Sodium Heparin Tubes for Processing

1. Label EDTA tube(s) according to the instructions in Section 5.4.2.
2. Collect 8-10 mL of bone marrow aspirate in each EDTA (purple top) tube(s).
3. Tubes should be inverted gently at least 3 times.
4. Tubes may be kept at ambient temperature after collection and during shipment

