### 5.4.1.2 Collection of Blood in ADC Tubes for Whole Blood Processing

1. Label ADC tubes according to the instructions in Section 5.4.2.
2. Collect up to 10 mL blood in each EDTA tube(s) and gently invert tube to mix.
3. Tubes should be inverted gently at least 3 times.
4. Tubes may be kept at ambient temperature after collection and during shipment

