### 1.2.1 Handling of Specimens(s)

#### Processing instructions

1. 30-60 minutes after sample collection (blood has clotted), centrifuge at ~1000-1300 x g (i.e., RCF, **not RPM**) for 10 minutes in swinging bucket (SW) or 15 minutes in a fixed angel (FA) rotor at 4°C in a refrigerated centrifuge. Make sure that the centrifuge reaches speed and is maintained throughout the entire spin.
2. Carefully remove tube from centrifuge.
3. Using a pipette, transfer equal aliquots of serum into 2-3 labeled 1.2 mL cryovials (e.g., preferred are external thread, conical self-standing vials like Corning™ 430658 or ), not exceeding ~1 mL per cryovial.
4. Label samples as (drug) (matrix) (purpose), including protocol number (#10417), unique patient ID assigned at registration, date of collection, draw time, time point, protocol time point, and initials.
5. Store serum samples at -70°C or below until shipment.

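### Appendix F 1.2 asks for clotted serum from heparin tubes for nivolumab PK, and Section 5.4 names EDTA where 5.1 requires sodium heparin or ACD

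*Combined protocol and SAP*

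**What the plan says.** **Nivolumab PK.** Appendix F 1.2 is headed as a serum procedure, but its first bullet reads "The plasma pharmacokinetic profile of nivolumab will be characterized by collecting blood samples". The next bullet specifies 3 mL draws into "tubes containing heparin as an anticoagulant (red top) at the time points specified below". The last bullet tells staff to invert the tube and "and then allow blood to clot for 30-60 minutes at room temperature before centrifugation". Section 1.2.1 of the appendix then says to "transfer equal aliquots of serum into 2-3 labeled 1.2 mL cryovials". Section 5.1 asks for 3 mL in a red-top vacutainer for nivolumab serum levels and does not mention heparin. Section 9.3 plans non-compartmental and population PK analysis of serum nivolumab.

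**Bone marrow.** Section 5.1 lists "10 mL of bone marrow aspirate in sodium heparin tubes (mandatory"). The heading of 5.4.1.1 also names sodium heparin. Step 1 under that heading labels EDTA tubes, and step 2 says "Collect 8-10 mL of bone marrow aspirate in each EDTA (purple top) tube(s").

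**Correlative blood.** Section 5.1 requires ACD tubes and marks them mandatory. The heading and step 1 of 5.4.1.2 say ADC, and step 2 says "Collect up to 10 mL blood in each EDTA tube(s) and gently invert tube to mix".

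**Labelling reference.** Both 5.4 procedures refer to Section 5.4.2 for labelling. The text runs from 5.4.1.3 straight to 5.5, and the labelling rules are in 5.3.2.

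**The concern.** These are collection instructions that site staff carry out, not background text. Section 5.4.1.3 gives no PK procedure of its own and simply points to Appendix F. Section 5.2.1 describes no collection kit that would settle the tube type; it says only that institutional supplies are used for shipping.

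Nivolumab PK serves secondary objective 1.2.8. Its pre- and post-infusion samples belong to a particular dose and cannot be drawn again later. A mistake could also go unnoticed for some time. Appendix F section 1.3 has PK samples stored to the end of cycle 1, and later nivolumab samples may be batched every 3 months. If some staff followed the word heparin and others the red-top cue, plasma and serum could both enter an analysis planned for serum.

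The marrow and ACD blood supply the correlative assays, including the residual-disease work under objective 1.2.6. There the question is whether the tube that staff are told to fill is the tube that the specimen table requires.

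**Working it through.** No statistical formula applies. The check is a comparison of the current text, followed by a count of the samples covered.

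**1. Tube and matrix, side by side**

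| Specimen | Section 5.1 | Procedure heading | Procedure steps |
|---|---|---|---|
| Nivolumab PK | Red top, serum | Serum (Appendix F 1.2) | Plasma profile; heparin, red top; clot; serum aliquots |
| Bone marrow | Sodium heparin, mandatory | Sodium heparin (5.4.1.1) | EDTA in steps 1 and 2 |
| Correlative blood | ACD, mandatory | ADC (5.4.1.2) | ADC in step 1, EDTA in step 2 |

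None of these conflicts comes from the summary of changes, a redaction or a broken table.

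**2. Can the steps be followed together?**

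- Nivolumab: no. Heparin is named as an anticoagulant, the next requirement is a clot, and the product is serum. The heading, the red-top cue, the clotting step, the aliquot and storage steps, 5.1 and 9.3 all agree on serum. Only the heparin phrase and the word plasma disagree.
- Marrow and blood: the steps can be carried out, but in a different tube from the one 5.1 requires.

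**3. Nivolumab samples covered per patient**

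The Appendix F schedule has two draws at each of four visits (cycle 1 day 14, induction cycle 2 day 1, maintenance cycle 1 day 1, maintenance cycle 3 day 14) and one draw at end of treatment or relapse.

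- Maximum: 4 × 2 + 1 = 9. This needs a patient who has induction cycle 2 and also reaches maintenance cycle 3.
- Remission after cycle 1, so no induction cycle 2: 3 × 2 + 1 = 7 at most.
- No response by cycle 3, so off study under the Schema and 9.1: 2 + 2 + 1 = 5 at most.

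**4. Illustrative ceiling for the 30 patients at the MTD**

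Assumptions: the share entering maintenance equals the 30% or 50% response rate in 9.1; every responder gives 9 samples; every non-responder gives 5.

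- At 30%: 9 × 9 + 21 × 5 = 81 + 105 = 186.
- At 50%: 15 × 9 + 15 × 5 = 135 + 75 = 210.

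Entry to maintenance also includes CRh, so the true share could differ. Nothing limits PK sampling to patients at the MTD, and 9.2 allows up to 42 patients. These figures are therefore not a total for the trial.

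**The case against.** The strongest reply is that the intended tube is easy to see. The heparin sentence closely follows the form of the K2 EDTA sentence in Appendix F 1.1 and looks like a carry-over. Almost everything else in the section points to serum. Appendix F also refers to a separate PK worksheet, which is not in the documents and may name the tube correctly. This stands as a limit on the consequence: the text can spoil samples, but the documents do not show that it will. It does not remove the contradiction from the instruction that sites are sent to.

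Three stronger readings are tempting, and the documents do not support them.

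- *That mandatory samples will fail to clot.* In 5.1 the word mandatory is attached to the marrow and the ACD blood. The nivolumab lines do not carry it, and the mandatory/optional entry for PK in 5.6 appears blank.
- *That about 270 nivolumab samples are at risk (9 × 30).* This gives every patient the maximum. Non-responders leave after cycle 3, and patients in remission after cycle 1 skip induction cycle 2.
- *That EDTA invalidates the marrow and blood assays and so threatens objective 1.2.6.* No section says that EDTA makes flow cytometry, cytogenetics, sequencing, tetramer analysis or methylation fail. Under 5.8.1 and 5.8.2, flow and cytogenetics are performed locally, with central review of the raw data or images. Section 5.5.1 has marrow for molecular sequencing sent in the usual way.

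It is also fair to say that the biomarker plan labels these assays exploratory.

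**Conclusion.** The point holds as an internal contradiction in operative text. For nivolumab PK, the Appendix F 1.2 steps cannot all be carried out as written, and they disagree with 5.1 and 9.3. The only outside premise is that blood in an anticoagulated tube does not clot. The instruction reaches up to 9 samples in the longest-treated patients and fewer in the rest. Actual loss depends on which cue a site follows and on the unseen worksheet.

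For marrow and correlative blood, the tube in the 5.4 steps differs from the one 5.1 requires at every such collection. Any loss of assay results there would be an inference that the documents do not establish.

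The effect is confined to secondary and exploratory material, chiefly objective 1.2.8. The DLT/MTD analysis, the sample size and the 30% versus 50% response rule do not depend on it. The text should be corrected because the remedy is cheap and the timed samples cannot be replaced.

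**What to change.** - **Appendix F 1.2:** delete the phrase about heparin as an anticoagulant, specify a red-top tube without anticoagulant, and change plasma to serum in the opening bullet on nivolumab.
- **5.4.1.1:** replace EDTA (purple top) in steps 1 and 2 with sodium heparin, as in 5.1.
- **5.4.1.2:** replace ADC in the heading and step 1, and EDTA in step 2, with ACD, as in 5.1.
- **Both 5.4 procedures:** change the labelling reference from the absent Section 5.4.2 to 5.3.2.
- **Before issue:** have each receiving laboratory confirm the tube and matrix for its specimens, and check that the PK worksheet agrees.

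The cost is a handful of wording corrections and a short confirmation from the laboratories. Treatment, visit schedule, sample size and analysis methods do not change.

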### 1.2.1 Handling of Specimens(s)

#### Processing instructions

1. 30-60 minutes after sample collection (blood has clotted), centrifuge at ~1000-1300 x g (i.e., RCF, **not RPM**) for 10 minutes in swinging bucket (SW) or 15 minutes in a fixed angel (FA) rotor at 4°C in a refrigerated centrifuge. Make sure that the centrifuge reaches speed and is maintained throughout the entire spin.
2. Carefully remove tube from centrifuge.
3. Using a pipette, transfer equal aliquots of serum into 2-3 labeled 1.2 mL cryovials (e.g., preferred are external thread, conical self-standing vials like Corning™ 430658 or ), not exceeding ~1 mL per cryovial.
4. Label samples as (drug) (matrix) (purpose), including protocol number (#10417), unique patient ID assigned at registration, date of collection, draw time, time point, protocol time point, and initials.
5. Store serum samples at -70°C or below until shipment.

### 1.3 Shipping of Specimen(s)

Specimens for venetoclax, OATP1B1 and nivolumab should be stored through the end of Cycle 1 and shipped as a batch by participant (more than one participant/shipment is acceptable if the site has >1 participant on-study). After cycle 1,

nivolumab samples can be shipped in batch every 3 months, or OSUCCC PhASR may contact the study team to request shipment off-schedule.

**Please ship 1 aliquots to the OSUCCC PhASR. Once receipt is confirmed, the back-up aliquot may be shipped. The back-up can be shipped at a later date with subsequent batches.**

Preparing the shipment

\*Samples should be stored in cardboard boxes (5 1/8" x 5 1/8" x 2", LxWxH) with dividers. (e.g., VWR Box item number is 82021-114; divider item number is 82007-154.)

\*Please organize the samples by Patient and Time point in the box.

\*Do not store in plastic bags (they break on dry-ice and labels will detach).

\*A copy of each of the pharmacokinetic sample collection forms (PK study worksheer) for the respective patients or a sample list should be included with each shipment. To prevent problems with illegible writing on tubes, consider numbering them (in addition to sample label) and numbering samples on the sample sheet.

\*Note the study number, PI, and the drugs used/to be measured.

\*A name, phone number and email address should be included with samples so that receipt can be acknowledged.

\*Please notify the lab by email ([[contact]](mailto:[contact])) at least 24 hours prior to shipment.

Shipping

\*All samples should be shipped via overnight express courier in insulated containers with enough dry ice to maintain the samples in a frozen state.

\*Overnight shipments should occur on Monday through Wednesday (Tuesday is the preferred day) except when the following day is a holiday.

## APPENDIX G: Medication Diary

### Important Instructions for your Venetoclax drug dosing:

Please call your clinic team with any questions related to taking your medication, or if you experience any side effects that you are concerned about.

Instructions: When taking Venetoclax as instructed to by your physician, record the date, time, and number of pills taken on the appropriate days.

Clinic phone: \_\_\_\_\_

Study coordinator name: \_\_\_\_\_ Phone number: \_\_\_\_\_
